The purpose of the research study is to challenge the state-of-the-science by developing evidence-based prosthetic and bicycle fit guidelines that optimize the biomechanics (injury), metabolic costs (effort), efficiency (function), satisfaction, and comfort of Veterans with transtibial amputations (TTAs). Thus, the proposed research is highly relevant to the rehabilitation of Veterans with TTAs. Following a TTA, Veterans who wish to restore their physical function have limited options for exercise. For example, running while using a prosthesis may increase the risk of secondary injury due to asymmetric and high loading patterns. Low impact exercise such as bicycling could facilitate normative function after amputation by improving cardiovascular fitness, muscle strength, endurance, and quality of life without incurring the high loads typical for walking and running for Veterans with TTAs. Bicycling as exercise could also prevent the deleterious effects of vascular disease and diabetes by improving cardiovascular function, controlling body weight, decreasing the rate of re-amputation, and improving quality of life for Veterans with TTAs. However, to maximize comfort and improve adherence to exercise, Veterans with a TTA likely need to adapt the fit of their prosthesis and bicycle. Optimizing bicycling, as exercise, for Veterans with TTAs through changes in prosthetic and bicycle fit (i.e. pylon length (PL), pedal attachment position (PAP) beneath the prosthetic forefoot versus the pylon, and crank arm length (CAL)) would improve rehabilitation by minimizing injury risk and discomfort, and maximizing function, thus facilitating the return to an active lifestyle and/or active duty. We propose to vary PL, CAL, and PAP in Veterans with unilateral TTAs. Then, we will develop evidence-based guidelines that optimize prosthetic/bicycle fit for Veterans with TTAs. These guidelines will allow Veterans with TTAs to enhance their physical function and quality of life by using bicycling for exercise.] Moreover, evidence-based prosthetic/bicycle fit guidelines will allow clinicians to more effectively fit Veterans with lower extremity amputations to bicycles, leading to shorter appointment times and fewer revisits due to enhanced function and reduced comorbidities.

Specific Aim 1. We will study 15 Veterans with unilateral TTAs to determine the effects of systematically varying PL, PAP beneath the prosthetic forefoot versus the pylon, and CAL for the affected leg (AL) on bicycling biomechanics, metabolic cost, and comfort/satisfaction. **Hypothesis 1.** A taller PL and shorter CAL for the AL compared to the unaffected leg (UL) and a PAP beneath the pylon compared to beneath the forefoot, will maximize mechanical power symmetry and reduce metabolic cost and muscle activity, and thus maximize efficiency and comfort/satisfaction during bicycling in Veterans with unilateral TTAs. Veterans with unilateral TTAs will ride a stationary bicycle ergometer at a fixed power output (1.5 W/kg) and complete a series of experimental trials over 2 days. On Day 1, we will perform a custom bike fit for each subject according to a protocol developed by Retül for non-amputees (Specialized Bicycle Components Inc., Boulder, CO). When fitting riders with TTAs, we will adjust the PL in combination with the socket and prosthetic foot of the AL to match the shank and foot length of the UL. Using this protocol, we will systematically vary saddle height and fore-aft position, handlebar vertical and fore-aft position, and alter cleat placement within the shoe for a forefoot PAP, using a conventional CAL of 172 mm. Then, we will measure the biomechanics (motion, forces, and muscle activity) and metabolic rates while subjects ride using the initial fit and three taller PLs for the AL in increments of 6.8 mm using a PAP beneath the prosthetic forefoot. Then, using the optimal (most efficient) PL, we will measure the biomechanics and metabolic rates while subjects ride using three shorter CALs for the AL in

decrements of 6.8 mm using a PAP beneath the prosthetic forefoot. On Day 2, we will repeat the protocol of Day 1, but have riders use a PAP beneath the pylon for their AL. We will randomize the order of days and trials within a day. [Because a prosthetic foot cannot flex and extend in a manner similar to the biological ankle, shortening CAL for the AL compared to the UL will reduce the geometric asymmetries between the AL and UL in bicyclists with a TTA. Childers and Kogler estimated that the UL shank and foot have 19.8 mm of displacement throughout the pedal stroke. Moreover, previous studies found differences in biomechanics and metabolic costs during bicycling based on CAL changes of 7.5-15 mm. Thus, we elected to measure the effects of four different CALs within a 19.8 mm range (0 mm, -6.6 mm, -13.2 mm, -19.8 mm) to establish how different prosthetic/bicycle configurations affect biomechanics and metabolic costs across CAL changes. To our knowledge, previous studies have not assessed the effects of changing PL. Thus, we chose to vary PL by the same magnitudes as CAL. We chose to increase PL and decrease CAL because if we lowered PL or increased CAL this would require us to lower the seat height for subjects to reach the bottom pedal position with their AL.

Specific Aim 2. We will synthesize and disseminate our findings from Specific Aim 1 into practical, evidence-based quantitative prosthetic/bicycle fit guidelines for Veterans with TTAs through a multiple regression and principal component analysis. These analyses will take into consideration the body mass, femur lengths, and UL shank and foot dimensions. We will disseminate our guidelines to prosthetists and clinicians in peer-reviewed public-access journals and through conferences/seminars.

II. Background and Significance:

Healthcare costs in the United States (US) now exceed \$3.2 trillion per year and many of the healthcare conditions at the root of these costs, such as Type 2 diabetes, are preventable through exercise. Due in large part to the prevalence of diabetes and recent military conflicts, there are over one million people in the United States who have a lower extremity amputation [1] and this number continues to grow. The incidence of diabetes is much greater in Veterans compared to the civilian population [2]; nearly one million Department of Veterans Affairs (VA) patients (1 of 5 patients) have diabetes. Over 25% of Veterans with an amputation attributable to vascular disease/diabetes will need an additional amputation [3]. It is projected that the number of people with diabetes who are living with limb loss will nearly triple and that the prevalence of limb loss will more than double by the year 2050 [4]. In addition, recent military conflicts such as Operation Iraqi Freedom (OIF) and Operation Enduring Freedom (OEF) have accounted for more than 1800 major limb amputations [5]. Due to functional impairments resulting from a lower extremity amputation, it is extremely important to advance rehabilitation practices that optimize the use of leg prostheses and increase exercise adherence so that Veterans and Service members with TTAs can regain the greatest possible level of health, function, and physical activity.

Due in part to the increased prevalence of amputations in Veterans and Service members, the Department of Defense (DOD) and VA Rehabilitation Directive has put forth an initiative that aims to dramatically improve and restore function in wounded Service members so that they have the choice to return to active duty or productive civilian employment. Our proposed research and development of optimized prosthetic/bicycle fit guidelines will enable VA prosthetists to improve rehabilitation, physical activity level, injury risk, and comfort of Veterans following amputation, thus helping to fulfill this initiative and having high potential impact. Our research addresses the *Prosthetics and Limb Loss* focus area within the Rehabilitation Research and Development service. This focus area serves to integrate advances in technology and rehabilitation to improve the lives of Veterans with an amputation. The utilization of evidence-based prosthetic/bicycle fit guidelines that optimize comfort, exercise adherence, and function will directly benefit Veterans with an amputation and the VA. More effective and optimized prosthetic and bicycle fitting will result in greater power output symmetry, reduced metabolic costs and injury risk, improved efficiency, and increased comfort. We aim to provide the best rehabilitation outcomes data regarding prosthetic devices and related clinical interventions.

Only 32-37% of people with TTAs engage in enough vigorous physical activity to elicit health benefits compared to 60% of non-amputees [6, 7]. Engagement in physical activity following an amputation is much lower than that of pre-amputation levels, and there are more barriers than

motivations for adopting and maintaining a physically active lifestyle in people with TTAs [6]. Generally, people with TTAs who return to recreational or sports activities choose to participate in less strenuous activities where a prosthesis is not required or the person is not functionally dependent on it. The barriers to engaging in physical activity include pain and physical limitations [6, 7]. Throughout rehabilitation, it has been suggested that clinicians and prosthetists should repeatedly encourage people with TTAs to stay/become physically active and provide information about strategies to reduce environmental barriers to sports participation, which could help people using assistive devices to overcome these barriers [8]. An optimal prosthetic/bicycle fit would reduce pain, physical limitations, and environmental barriers to exercise and could thus promote physical activity in Veterans with TTAs. Low impact aerobic exercise such as bicycling could facilitate normative function after amputation by improving cardiovascular fitness, muscle strength, endurance, and quality of life for Veterans with TTAs without incurring the high joint and tissue loads inherent in walking and running [9]. Bicycling for exercise could also prevent the deleterious effects of vascular disease and diabetes by improving cardiovascular function, controlling body weight, decreasing the rate of re-amputation, and improving quality of life for Veterans with TTAs. However, a previous study estimated that only 11.5% of Veterans with TTAs use bicycling for exercise [7]. It is likely that bike and socket discomfort/pain and the increased potential for secondary musculoskeletal injury due to the lack of a proper bike fit discourage Veterans with TTAs from using bicycling for rehabilitation and exercise.

Riding a bicycle with a TTA presents novel challenges compared to non-amputees. People with TTAs lack the muscles that plantarflex and dorsiflex the ankle joint to assist them in the pedaling motion of bicycling. These muscles act to stabilize the ankle and transfer force and energy to and from the pedal [9]. Bicyclists with TTAs have increased muscle activity variability in the two-joint muscles of both legs and a longer duration of gastrocnemius activity in the unaffected leg (UL) compared to non-amputees [9]. Although the role of the ankle in bicycling is disputed, research has shown that the ankle position throughout the pedal cycle influences the application of mechanical power generated by the leg [10]. Pierson-Carey et al. [10] immobilized the ankle in non-amputees and found that during the down-stroke of the pedaling cycle, power output decreased compared to a fully mobile biological ankle joint. The application of force on each bicycle pedal influences mechanical power production, and therefore affects overall efficiency. Thus, optimizing PL, PAP, and/or CAL would improve mechanical power output symmetry and efficiency in individuals with TTAs during bicycling.

Research that examines the underlying changes in biomechanics and metabolic costs that are elicited by people with TTAs when bicycling with different prosthetic/bicycle configurations would facilitate improved rehabilitation [9] and exercise adherence. Changes in body positioning due to changes in PL, CAL, and PAP likely affect the overall function, comfort, and injury risk of bicyclists, but the effects of these changes are complex and likely more complicated due to different limb geometry in bicyclists with TTAs [9]. The asymmetric structural differences between the legs of bicyclists with a TTA result in dramatically asymmetric torque and mechanical work during bicycling; mechanical work asymmetry can be up to 7x greater in bicyclists with a TTA compared to non-amputees [9]. Presumably, the magnitude of force asymmetry between the AL and UL of people with unilateral TTAs is influenced by leg length discrepancies and the loss of the muscles that act across the ankle joint. To our knowledge, no previous research has systematically varied PL and determined the effects on bicycling biomechanics and performance. Because a person with a TTA does not have a functional ankle joint, the PL combined with prosthetic foot build height may need to be taller than the height of the foot and shank of the UL to improve mechanical power symmetry and lower metabolic cost. Further, despite previous research, it remains unclear how alterations to a bicycle's CALs affect the efficiency of people without and with TTAs [9]. When manipulating CALs for both legs of non-amputee cyclists, Morris & Londeree [11] found that each individual had a specific CAL that resulted in the greatest efficiency. However, with a relatively small sample size (n=6), they were unable to determine any relationships between the rider's leg lengths and optimal CALs. Koutny et al. [12] investigated the effects of using three different CALs (160, 167.5, and 175 mm) on one high-caliber cyclist with a TTA and found that at a fixed mechanical power output, the rider's leg muscle activity was minimized with the medium CALs (167.5mm), but the average torque applied to the cranks was unchanged across CALs. It is unclear

whether Koutny et al. manipulated CALs for both legs or just changed the CAL for the affected leg (AL). Regardless, reduced muscle activity suggests a lower metabolic cost and thus improved efficiency during bicycling. Childers and Kogler [13] compared the knee and hip joint kinematics and kinetics of 8 cyclists with TTAs with CALs of 172 mm for each leg compared to a CAL of 172 mm for the UL and a CAL of 162 mm for the AL. With asymmetric CALs, knee and hip joint angles and range of motion were more symmetric between legs, but joint kinetics (torque and work) did not change. They suggest that a CAL of 160 mm for the AL would be advantageous for joint angle and range of motion symmetry. However, it is not clear if Childers and Kogler [13] matched the AL height of the pylon and the prosthetic foot to the UL height of the shank and biological foot. Shortening the CAL for the AL could reduce the geometric asymmetry between legs and thus result in more symmetric knee and hip joint angles.] A pilot study (n=3) by Childers et al. [9] found that a 15 mm shorter CAL for the AL versus UL may improve the force symmetry of people with TTAs and thus improve their power output symmetry. They reported that shortening the CAL for the AL versus UL reduced mechanical work asymmetry by 53% [9]. Further, with a shortened CAL on the AL compared to UL, riders reported improved comfort [9]. [Previous studies that varied the anterior-posterior position of the bicycle cleat (PAP) found no effects on metabolic costs for non-amputees, but did find a reduction in gastrocnemius, soleus, and tibialis anterior muscle activations with a forefoot position compared to a heel placement. Childers et al. [9] suggest that the effective prosthetic length, the distance from the knee center to the pedal spindle, should be equivalent between legs in cyclists with unilateral TTAs to minimize kinematic asymmetries. However, no studies to date have determined the optimal PAP or calculated the optimal effective prosthetic length.

Moreover, it is unclear how changes in each prosthetic and bicycle configuration, such as PL, PAP beneath the prosthetic forefoot versus the pylon, and CAL (Fig. 1) affect the biomechanics, metabolic cost, and comfort/satisfaction of Veterans with TTAs. Thus, we will quantify the effects of systematic changes in PL, PAP, and CAL on the bicycling performance of Veterans with unilateral TTAs to develop novel evidence-based guidelines that optimize prosthetic and bicycle fit. The proposed analysis is innovative in that we will assess and optimize the effects of each geometrical change in the same person and use the overall results to develop guidelines for bicycle/prosthetic fit. Further, we will examine the underlying mechanisms, such as changes in joint kinematics and kinetics, and muscle activity magnitude and timing that elicit these effects to determine the unique adaptations made by bicyclists with TTAs. Optimized prosthetic and bicycle fit guidelines will allow Veterans with TTAs to ride longer with less effort, pain/discomfort, and injury risk, which would lead to improved rehabilitation and quality of life. Reducing the metabolic cost required for bicycling is clinically significant because an excessive sense of effort and fatigue discourages physical activity [14]. The prosthesis/bike fit guidelines resulting from our research will also determine the configuration that maximizes symmetry between legs, which could reduce injury risk and pain, and maximize function through improved mechanical power output and efficiency. Moreover, evidence-based prosthetic/bicycle configuration guidelines will allow clinicians to more effectively treat Veterans with TTAs, leading to shorter appointment times and fewer revisits due to enhanced function and reduced comorbidities.

[figure not shown]

Figure 1. A pylon connects the socket of the affected leg of a cyclist with a transtibial amputation to the prosthetic foot, which attaches to the pedal. The crank arm links the pedal to the chain ring, allowing power transmission to the rear wheel. Adjustments to pylon length (PL), pedal attachment position (PAP) and crank arm length (CAL) likely affect mechanical power output, metabolic cost and comfort/satisfaction.

III. Preliminary Studies/Progress Report:

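### The pylon length carried into the crank rides is each rider's best single ride, and the plan does not say how that pick is handled: rider optima would favour taller pylons by noise, and the crank contrast is biased against shorter cranks

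*Combined protocol and SAP*

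**What the plan says.** Specific Aim 1, repeated in Study Design and Research Methods, has each subject "ride using the initial fit and three taller PLs for the AL in increments of 6.8 mm". It continues: "Then, using the optimal (most efficient) PL, we will measure the biomechanics and metabolic rates while subjects ride using three shorter CALs". The second day repeats this with the other pedal attachment position (PAP): "On Day 2, we will repeat the protocol of Day 1, but have riders use a PAP beneath the pylon for their AL". That makes 4 + 3 = 7 listed rides per day and 14 in all, with no setting ridden twice.

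Standard is the end point of both grids. The reason given is practical: "if we lowered PL or increased CAL this would require us to lower the seat height". Hypothesis 1 points the same way as the grids: "A taller PL and shorter CAL for the AL compared to the unaffected leg (UL").

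Under Outcome Measure(s), efficiency is fixed mechanical power divided by metabolic power averaged over minutes 3.5 to 5.5 of one 6-minute ride. The same section names repeated-measures ANOVA with Bonferroni correction to find the best combination, linear mixed models for Aim 1, and multiple regression and/or principal components for Aim 2. The Aim 2 response is not defined. Background and Significance says "we will assess and optimize the effects of each geometrical change in the same person and use the overall results to develop guidelines".

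**The concern.** Because the crank rides follow in the same session at the chosen PL, the choice has to be made then, and so apparently rider by rider. It rests on one noisy value per setting. No replicate ride, confirmation ride, minimum difference or shrinkage is described.

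Two things are at stake.

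- **Rider optima.** The best of four values on a grid that starts at standard can only be standard or taller. If these picks, or gains read from the rides that made them, become Aim 1 results or the Aim 2 response, the fitting guideline could recommend a taller pylon because of noise.
- **The crank comparison.** The winning PL ride won partly by luck. If it also serves as the 172 mm reference, the shorter cranks are compared with a value that is too high on average.

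**Working it through.** **The plan's own figure.** None is given for the selection step. The nearest is a value above 0.86 for a 10% difference in efficiency with 15 riders (Data Analysis Plan). It is labelled an effect size, although the PEQ value in the same list, 0.44, is called power under Potential Scientific Problems. The SD behind 0.86 is not stated, so it cannot be reproduced. Read as power of a two-sided paired t-test at 0.05, it needs a standardised difference of 0.845, so SD of the difference = 10% / 0.845 = 11.8%.

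**Inputs.** From the plan: 15 riders; PL offsets 0, 6.8, 13.6 and 20.4 mm; three shorter cranks; one ride per setting; two PAPs. Assumed: no true effect of any setting, and independent ride noise of equal variance. SD below means the ride-to-ride SD of efficiency within a rider. The plan gives no value for it.

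**(a) Rider optima for PL**

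1. All four rides are equally likely to win: P(taller) = 3/4 = 75%.
2. Mean chosen PL = (0 + 6.8 + 13.6 + 20.4)/4 = 10.2 mm. The Aim 1 rationale uses steps of 6.6 mm instead ("0 mm, -6.6 mm, -13.2 mm, -19.8 mm"), which would give (0 + 6.6 + 13.2 + 19.8)/4 = 9.9 mm. The two step sizes must be reconciled, but the probabilities do not depend on them.
3. P(at least 8 of 15 riders taller) = P(Binomial(15, 0.75) ≥ 8) = 0.983.
4. Expected gain over the standard ride = E[max of k standard normals] = ∫ x·k·φ(x)·Φ(x)^(k−1) dx. This is 1.03 SD for k = 4, 1.35 SD for k = 7 and 1.70 SD for k = 14.
5. In percent, for an assumed SD of 1% to 8%: best of 4 gives 1.0% to 8.2%, and best of 14 gives 1.7% to 13.6%.
6. If standard is truly better than every taller PL by 0.5 or 1 SD, a taller one is still picked for 61% or 45% of riders.
7. Without selection, repeated-measures ANOVA on the four PL levels has a simulated type I error of 4.9%.

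**(b) Cranks, with the winning PL ride as the 172 mm reference**

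1. Expected contrast, mean of three shorter cranks minus reference = 0 − 1.03 = −1.03 SD.
2. Variance per rider = 1/3 (mean of three rides) + 0.492 (variance of the maximum of four normals) = 0.825, so the SD is 0.908.
3. With 15 riders the standard error is 0.908/√15 = 0.234, so a typical t is about −1.03/0.234 = −4.4. The critical value is ±2.14 (14 df).
4. Simulated under no effect, the contrast is significant against shorter cranks in 98.6% of trials for one PAP and about 100% with both PAPs averaged. ANOVA over the four crank levels has type I error of about 90%.
5. A best-of-seven pick within a PAP assigns a shorter crank to 3/7 = 43% of riders, so 57% stay at 172 mm.
6. If 172 mm were ridden again at the chosen PL, the contrast would have no bias and type I error of 4.9%.

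**PAP.** Noise picks either position 50% of the time.

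**Check of the remedy.** Under no effect, a model using all 14 rides, with rider intercepts and common PL and CAL slopes, had type I error of about 5% for both slopes and mean slopes near zero. When riders truly differ in slope, the common-slope model reached 20% to 25%. Random rider slopes kept it at 3% to 6% with near-zero bias. That last comparison is small (150 trials per scenario, with convergence warnings).

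**The case against.** The strongest reply is that the most efficient PL is only an in-session rule for which pylon goes forward, while inference rests on ANOVA and mixed models. Potential Scientific Problems also speaks of significant differences from standard, and of checking robustness across participants should standard prove best. Much of this stands. The ANOVA on the four PL levels is sound, and the one-sided grid does no harm by itself.

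Two stronger readings are tempting, and the documents do not support them.

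- A reader might infer that the plan will test mean chosen PL against zero, or the best of 14 rides against standard, so that noise alone confirms Hypothesis 1. No section commits to either. The sentence in Background and Significance about optimising within the same person can also describe ordinary within-subject testing.
- A reader might infer that the one-sided crank grid favours shorter cranks in the same way. As written it does not: most riders stay at 172 mm under noise, and the mean contrast runs against Hypothesis 1.

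The reply leaves two gaps. The plan never says how the analysis treats the data-driven pick, and it never defines the Aim 2 response. Nor does planning ANOVA or mixed models protect the crank comparison if it uses only the rides at the chosen PL.

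**Conclusion.** The point holds in two parts, and the severity is should-fix.

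(a) is conditional. If per-rider best settings, or gains from the rides that picked them, are reported or fed to Aim 2, noise alone assigns a taller pylon to 75% of riders (mean +10.2 mm) and shows gains of 1.03 to 1.70 SD. The 75% does not depend on the size of the noise. The percent gains do, and the documents give no ride-to-ride SD.

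(b) concerns the crank comparison as the rides are listed. Using the winning ride as the 172 mm reference biases it by about 1 SD against shorter cranks, and it is almost always falsely significant under no effect.

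The figures rest on independent, equal-variance ride noise. Both parts rest on a per-rider pick, which is inferred from the session sequence and not stated outright. Part (b) also rests on there being no second 172 mm ride at the chosen PL. Other outcomes, such as symmetry, muscle activity and comfort, are affected only as far as their noise follows that of efficiency, or if they too are summarised by best ride.

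**What to change.** Keep the grid and the in-session pick, and add to the analysis plan:

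- Estimate PL and CAL effects on efficiency from one linear mixed model using all rides of both days, including the PL rides that were not selected. Enter PL and CAL in mm, with PAP and random rider intercepts and slopes. Reconcile the 6.8 mm and 6.6 mm steps first.
- Do not contrast shorter cranks with the selected ride alone.
- Claim a benefit of taller pylons or shorter cranks only if the confidence interval for that slope excludes zero.
- Define the Aim 2 response as the model-predicted (shrunken) rider value, not the best observed ride.
- Report any gain over standard from the model, or by leave-one-rider-out: choose on 14 riders and evaluate on the 15th.
- If observed optima are tabulated, print the no-effect expectation for PL (75%, +10.2 mm) beside them.

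The cost is analysis-plan wording and a few lines of code, with no extra rides or riders. Reported gains will be smaller, and random slopes widen the intervals somewhat with 15 riders. The model may also need simplifying if it fails to converge. It does not remove drift between the PL rides and the crank rides that follow them, so that limit should be stated.
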